9. SAFETY ANALYSES

Safety analyses include exposure to study treatment, treatment-emergent adverse events (TEAEs), clinical laboratory parameters, electrocardiograms (ECGs), vital signs, and any abnormal findings observed during physical examinations after study enrollment and through discontinuation of study treatment or within 30 days after the discontinuation of study treatment. Data after a patient begins commercial OCALIVA will be excluded. Safety analyses will be performed using the Safety Population including by treatment groups. No inferential comparison of safety endpoints will be performed, unless otherwise specified.

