9.2.1. Treatment-Emergent Adverse Events

A TEAE is any event not present prior to the initiation of the IP or any event already present that worsens in either intensity or frequency following exposure to the IP or within 30 days after the discontinuation of the study treatment.

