9.2.4. TEAE Analyses

The number of events and counts and percentages of unique subjects experiencing a TEAE and TEAEs by PTs and SOC in the following categories will be presented for the Safety Population:

- TEAEs

- TEAEs by highest severity (mild, moderate, severe): At each level of subject summarization, a subject is classified according to the highest severity if the subject reported 1 or more events. AEs with missing severity will be considered severe for this summary.
- Serious AEs
- Adverse events of special interest
- AESIs by highest severity (mild, moderate, severe): At each level of subject summarization, a subject is classified according to the highest severity if the subject reported 1 or more events. AEs with missing severity will be considered severe for this summary.
- TEAEs leading to study treatment discontinuation: This is a subset of the AEs where action taken with study treatment is checked as “Drug withdrawn” or where “Subject Discontinued from Study” is checked.
- TEAEs leading to study treatment interruption: This is a subset of the AEs where action taken with study treatment is checked as “Drug interrupted”.
- TEAEs leading to study treatment dose reduction: This is a subset of the AEs where action taken with study treatment is checked as “Dose reduced”.
- Deaths: This is a subset of the AEs where “Fatal” is checked.
- Subject incidence of TEAEs by MedDRA SOC, PT, and closest relationship to investigational product (Related/Not Related). Related AEs are those with relationships reported by the Investigator as “Definite,” “Probable,” or “Possible,” and unrelated AEs are those with relationships reported as “Unlikely” or “Not Related.” At each level of subject summarization, a subject is classified according to the closest relationship if the subject reported 1 or more events. AEs with a missing relationship will be considered related for this summary.

Summaries will be sorted in order of decreasing frequency in the treatment arm. Summaries will also be presented by MedDRA SOC and PT, sorted in alphabetic order of SOC and then in order of decreasing frequency in the treatment arm.

Exposure-adjusted incidence of TEAEs will also be provided by SOC and PT. Each individual subject year on study will be derived as the last known date during the study minus the first dose date plus 1 divided by 365.25 days/year.

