Exposure-adjusted incidence rates will additionally be provided by SOC and PT for “on-risk” AEs. An on-risk adverse event (ORAE) is any event not present prior to the initiation of the IP or any event already present that worsens in either intensity or frequency following exposure to the IP or within 30 days after the discontinuation of the regularly-scheduled study visits. As some subjects may be on commercial OCALIVA after discontinuing study treatment and prior to discontinuing regularly scheduled study visits, ORAE events will be summarized prior to initiation of commercial OCALIVA.

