9.8. Subgroup Analyses of Safety

Demographics and baseline disease characteristics ([Section 6](#)), exposure to study treatment ([Section 9.1](#)) and the adverse events ([Section 9.2](#)) analyses listed below will be presented for the baseline disease stage subgroup described in [Section 8.7](#).

The number of events and counts and percentages of unique subjects experiencing a TEAE and TEAEs by PTs and SOC in the following categories will be presented:

- TEAEs
- Serious AEs
- Adverse events of special interest
- TEAEs leading to study treatment discontinuation
- Deaths

Exposure-adjusted incidence of TEAEs will also be provided by SOC and PT.

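### Exposure-adjusted TEAE rates count events only to 30 days after the last dose but divide by all time on study, so the rates are understated

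*SAP*

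**What the plan says.** **Numerator.** Section 9.2.1 defines a TEAE as a new or worsening event "following exposure to the IP or within 30 days after the discontinuation of the study treatment". The opening of Section 9 sets the same window for safety data in general and adds: "Data after a patient begins commercial OCALIVA will be excluded".

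**Denominator.** Section 9.2.4 provides exposure-adjusted TEAE incidence by SOC and PT. The years contributed by each subject are called years on study, and a subject's time "will be derived as the last known date during the study minus the first dose date plus 1 divided by 365.25 days/year". There is no cut at last dose plus 30 days and none at the start of commercial OCALIVA. Section 9.1 has a duration of exposure built from first and last IP dose, but the rate does not use it.

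**On-risk events.** Section 9.2.4 adds rates for on-risk AEs, with a longer event window that runs to "within 30 days after the discontinuation of the regularly-scheduled study visits" and takes only events before commercial OCALIVA. No separate denominator is given for them.

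**Subgroups.** Section 9.8 repeats the TEAE rate by baseline disease stage: "Exposure-adjusted incidence of TEAEs will also be provided by SOC and PT".

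**Follow-up.** Section 3 expects subjects who stop IP to be followed to study closure, or at the sponsor's discretion, and plans a minimum of about 6 years of follow-up.

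**The concern.** A rate is interpretable only if its person-time is the time during which a counted event could have occurred. Here the two parts have different end dates. A subject who stops IP and stays in follow-up adds years to the denominator but, after 30 days, cannot add a TEAE to the numerator.

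The SAP itself expects such time. Section 8.1.1 will tabulate patient-years accrued after IP discontinuation and after starting commercial OCALIVA. Section 14.1 gives high discontinuation as part of the reason for stopping early, and Section 6.4 of the interim SAP reports treatment discontinuation above expectation.

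At stake is the table a reader would use to compare TEAEs in general, including hepatic events and pruritus, when time on drug is unequal. It is also the table carried into the on-label and contraindicated subgroups. Rates labelled as exposure-adjusted would in fact be adjusted for time on study.

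**Working it through.** The SAP states no TEAE rate and no person-time total, so there is no figure of its own to reproduce. The check is algebra on its definitions.

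**Inputs from the SAP**
- Event window: first dose to 30 days after stopping IP, cut at commercial OCALIVA (Sections 9 and 9.2.1).
- Study time: first dose to last known date (Section 9.2.4).

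**Assumptions, because the SAP gives no time on drug by arm**
- Constant event rate λ inside the window; all events counted.
- W = years in the event window; F = years of study time.

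**Formulas**
- Expected events = λW.
- Rate as written = λW/F. Rate with matched person-time = λW/W = λ.
- Share of the true rate kept = W/F.
- Apparent OCA:placebo ratio = true ratio × (share kept in OCA)/(share kept in placebo).

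**F = 4 years in both arms**
- W = 2.0: 2.0/4 = 0.50, understated by 50%.
- W = 2.5: 2.5/4 = 0.625, understated by 37.5%.
- Equal true rates, OCA 2.0 and placebo 2.5: 0.50/0.625 = 0.80.
- Reversed, OCA 2.5 and placebo 2.0: 0.625/0.50 = 1.25.
- Equal W in both arms: the ratio is right, but both rates are too low.

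**F = 6 years, with T years on drug and the 30 days added (30/365.25 = 0.082 years)**
- T = 2: 2.082/6 = 0.347. T = 3: 3.082/6 = 0.514. T = 6: 1.00, no dilution.
- True ratio 1.5, OCA T = 2 and placebo T = 3: 1.5 × 0.347/0.514 = 1.01.
- Reversed: 1.5 × 3.082/2.082 = 2.22.

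**If the numerator is subjects with at least one event** (assumed rate 0.2 per year, F = 4)
- W = 2.0: (1 − e^−0.4)/4 = 0.330/4 = 0.082, which is 59% below 0.2.
- W = 2.5: (1 − e^−0.5)/4 = 0.393/4 = 0.098, which is 51% below 0.2.
- Ratio 0.082/0.098 = 0.84. The ratio is distorted a little less than with all events counted, but the level is further off, partly because time also runs on after the first event.

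**With matched person-time** and all events counted, the share kept is 1.00 in each arm, and a true ratio of 1.5 stays 1.5.

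**The case against.** The strongest reply is that little depends on these rates. Section 9 rules out inferential comparison of safety endpoints unless specified, and none is specified here. Event counts and subject percentages stand beside the rates and are untouched by the denominator. That is correct and limits the weight of the point, but a descriptive rate still has to estimate something.

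Second, the last known date is not defined in Section 9.2.4, and the exclusion of data after commercial OCALIVA could be read as cutting person-time too. That reading is possible, but Section 9.2.4 does not state it, and off-drug time without OCALIVA would remain in any case.

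Third, high discontinuation may partly mean leaving the study altogether, in which case follow-up past the window is short and dilution small. This is fair, and it is why the size can only be shown as a range.

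Fourth, the on-risk analysis covers off-drug time while regular visits continue. It does so for a different set of events and leaves the TEAE rate as it is. Because no denominator is stated for it, a mismatch there is an inference, and the gap would be narrower.

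A reader might also infer that the error flatters OCA. The documents do not support that. They give no discontinuation by arm, and the interim SAP (Section 3) uses as its example placebo subjects who stop and start commercial OCA, which would push the ratio the other way.

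**Conclusion.** The mismatch is in the text. Applied as written, Section 9.2.4 understates TEAE rates in any arm where follow-up outlasts the event window, and Section 9.8 carries this into the disease-stage subgroups. Under a constant rate with all events counted, the share kept is window time over study time: 50% to 62.5% for the assumed 2.0 to 2.5 of 4 years, and 100% only where nobody is followed past the window.

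The between-arm ratio is distorted only if the share of follow-up outside the window differs by arm. For those same assumptions, equal true rates would show 0.80 or 1.25, and the direction is unknown.

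It would be too strong to call this the SAP's only safety comparison that allows for unequal time. Section 9.3 compares adjudicated MACE by log-rank and Cox methods, and that analysis is unaffected. The point concerns descriptive TEAE rates; it does not touch any hypothesis test.

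**What to change.** In Section 9.2.4, end each subject's TEAE person-time at the earliest of last dose plus 30 days, the day before commercial OCALIVA starts, and the last known date during the study. Define that last date. State that Section 9.8 uses the same person-time.

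For on-risk AEs, state a denominator: the same rule, with last regular visit plus 30 days in place of last dose plus 30 days.

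Say whether the numerator is all events or subjects with a first event of the term. Stop person-time at the first event only in the latter case. If all events are counted, omit that cut, since it would inflate rates for recurrent terms.

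The cost is SAP wording and one derived end date per analysis. The dates are already collected, and Section 4.2.2 of the interim SAP already has a rule for the start of commercial OCA that can be reused.

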9.3. Adjudicated Cardiovascular Events

Major Adverse Cardiovascular Events (MACE) (defined as death, myocardial infarction, and stroke) are included in the Cardiovascular Adjudication Committee Charter for adjudication. The adjudication of these events will be handled separately from the adjudication of events for assessment of the primary clinical composite outcome endpoint in this study.

Adjudicated MACE is a time-to-event endpoint and will be summarized for the Safety Population.

OCA and placebo treatment groups will be compared using the log-rank test stratified by the randomization stratification factors. In addition, the hazard ratio and 95% CI will be determined based on a Cox regression model stratified by randomization strata to estimate the magnitude of the effect.

The number and percent of subjects censored and with events will be presented. Descriptive statistics will be presented for the time-to-event.

Kaplan-Meier (KM) estimates of the distribution of the time-to-event will be tabulated and graphed by treatment group. The tabulation will include the KM estimate of the 25th, 50th (median), and 75th percentiles and corresponding 95% CIs, where the percentiles can be estimated. KM tabulations will present time to event in days; KM graphs will present time to event in months. The hazard ratio and 95% CI will be estimated based on a Cox regression model stratified by randomization strata.

Only adjudicated events will be included in analyses. Subjects without any documentation of events will be censored at the date of last contact. For subjects with more than one event, the earliest of the event dates will be used.

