2.1.1. Primary Objective

The primary objective of this study is to compare the effect of obeticholic acid (OCA) to placebo, in conjunction with established local standard of care, on clinical outcomes in subjects with primary biliary cholangitis (PBC) as measured by time to first occurrence of the following adjudicated events, derived as a composite event endpoint (including all Group 1 – Group 3 events).

Group 1:

- Death (all-cause)
- Liver transplant
- Hospitalization (as defined by a stay of 24 hours or greater) for new onset or recurrence of:
 - Variceal bleed
 - Hepatic encephalopathy (as defined by a West Haven score of ≥ 2)
 - Spontaneous bacterial peritonitis (confirmed by diagnostic paracentesis OR presence of $>250/\text{mm}^3$ polymorph leucocytes [PMNs] in the ascitic fluid)
 - Bacterial empyema (confirmed by diagnostic thoracentesis OR presence of $>250/\text{mm}^3$ PMNs in the pleural fluid)
- Uncontrolled or refractory ascites (requiring large volume paracentesis)
- Portal hypertension syndromes:
 - Hepatorenal syndrome (as defined by International Ascites Club [[Angeli 2019](#)])
 - Portopulmonary syndrome
 - Hepatopulmonary syndrome

- Model of end-stage liver disease (MELD)-Na score ≥ 15 if MELD-Na < 12 at baseline
- MELD score ≥ 15 if MELD-Na ≥ 12 at baseline

Group 2:

- Progression to decompensated liver disease (for subjects without decompensation at baseline), prioritized as follows:
 - New onset of:
 - Hepatic hydrothorax
 - Variceal bleeding
 - Ascites requiring treatment with sodium restriction, diet modification, or diuretics
 - Hepatic encephalopathy requiring lactulose and/or rifaximin
 - New onset of:
 - Child-Pugh ≥ 7
 - Total bilirubin > 3 mg/dL

Group 3:

- Progression to clinical evidence of portal hypertension without decompensation (for subjects without decompensation or clinical evidence of portal hypertension at baseline)
 - Endoscopic evidence of portal hypertension without bleeding
 - Gastroesophageal varices (requiring banding or progression to large varices if no or small varices were observed at baseline)
 - Portal hypertensive gastropathy
 - Platelets $< 150 \times 10^9/L$ with splenomegaly and/or with transient elastography > 15 kPa

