3. SUMMARY OF STUDY DESIGN

[figure not shown]
This Phase 4, double-blind, randomized, placebo-control, multicenter study will evaluate the effect of OCA on clinical outcomes in subjects with PBC who are at higher risk of liver-related clinical complications.

Eligible subjects will have a diagnosis of PBC with bilirubin levels $>ULN$ and $\leq 5x ULN$ and/ or $ALP > 3x ULN$. Subjects will be screened twice during a 1- to 8-week Screening period prior to entering the study to allow for the collection of repeat serum chemistry samples (at least 2 weeks apart) to confirm pretreatment alkaline phosphatase (ALP) and total bilirubin values.

Investigational product (IP) will be taken orally, once daily for the majority of subjects; dose and frequency will be modified for subjects with cirrhosis (including subjects progressing to cirrhosis during the study) and classified as Child-Pugh B or C. The randomization will be stratified by ursodeoxycholic acid (UDCA) treatment (yes/ no) and baseline bilirubin categories ($>$ upper limit of normal [ULN]/ $\leq ULN$). A minimum of 30% of subjects will have elevated bilirubin ($>ULN$) at Screening.

The study is event driven and will continue until approximately 127 adjudicated primary endpoint events have been accrued in unique subjects, or until the Sponsor (eg, based on a recommendation from the Data Monitoring Committee (DMC)) terminates the study. Subjects are expected to be followed for a minimum of approximately 6 years. Figure 1 below displays the study design diagram. Schedules of study procedures are outlined in Table 1 (Screening to Month 12) and Table 2 (Year 2 to End-of-Study Endpoints) of the study protocol, where more details are provided.

Figure 1: Schematic Diagram Study 747-302

EOS = end of study; M = month, OCA = obeticholic acid; ULN = upper limit of normal
 Initial dose titration of investigational product should occur at the Month 3 visit, or any study visit thereafter for subjects on all dosing regimens, based on tolerability and biochemical response (Up-titration should be considered when ALP and/ or total bilirubin are $>ULN$). Subsequent dose titration(s) for subjects classified as Child Pugh B or Child-Pugh C and following a modified dosing schedule may occur no earlier than 6 weeks after the previous dose titration.

Dosing frequency will be determined by the presence or absence of cirrhosis and, if cirrhosis is present, by Child-Pugh Score as described below:

	Planned Dosing Regimen	

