8.3. Additional Secondary Efficacy Endpoints

8.3.1. Time to Event Analyses

The following time-to-event secondary efficacy analyses will compare OCA versus placebo using the ITT population:

- Time to each relevant component of the primary efficacy endpoint
- Time to development of varix/varices
- Progression to cirrhosis
- Time to occurrence of HCC
- Time to liver-related death
- Time to liver-related death or liver transplant
- Time to liver-related death, liver transplant, or MELD score ≥ 15

All additional secondary time-to-event outcomes with the exception of death will be analyzed in the context of competing risks.

For the following secondary endpoints, liver transplant and death will be considered competing risks:

- Time to each relevant component of the primary efficacy endpoint, with the exception of death and liver-transplant
- Time to development of varix/varices

- Progression to cirrhosis
- Time to occurrence of HCC

For the following secondary endpoints, death will be considered a competing risk:

- Time to liver-transplant

For the following secondary endpoints, non-liver-related death will be considered a competing risk:

- Time to liver-related death
- Time to liver-related death or liver transplant
- Time to liver-related death, liver transplant, or MELD score ≥ 15

Competing risk outcomes will be compared and summarized through a cumulative incidence function (CIF). Gray's (1988) non-parametric test will be used to compare the CIFs of the two treatment groups. Hazard ratios and their 95% confidence intervals will be computed following the Fine and Gray model (1999). Fine and Gray's hazard model can be fit in SAS version 9.4 and higher by specifying eventcode option in PROC PHREG.

Progression to cirrhosis will be assessed in the subset of subjects considered noncirrhotic at Baseline using available medical history, clinical, and laboratory assessments as well as baseline transient elastography (TE), where available. Specifically, subjects with no clinical, laboratory, or radiological evidence of cirrhosis at baseline and/or a TE liver stiffness of < 16.9 kPa (Corpechot 2012) will be considered noncirrhotic. Progression to cirrhosis will be assessed by the development of clinical, laboratory, or radiological evidence of cirrhosis and/or when liver stiffness increases to ≥ 16.9 kPa during the study in which case histological progression to cirrhosis should be confirmed by biopsy unless not medically indicated.

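### Section 9.3 does not limit the death component of MACE to cardiovascular death, so the SAP's only inferential safety comparison mixes cardiovascular harm with other mortality

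*SAP*

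**What the plan says.** Section 9 rules out inferential comparison of safety endpoints unless the SAP specifies otherwise. Section 9.3 is the one place in the safety chapter that does. It states: "Major Adverse Cardiovascular Events (MACE) (defined as death, myocardial infarction, and stroke) are included in the Cardiovascular Adjudication Committee Charter for adjudication". That charter is not among the documents. On the test it says: "OCA and placebo treatment groups will be compared using the log-rank test stratified by the randomization stratification factors". A stratified Cox hazard ratio with 95% CI is added.

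Two counting rules follow: "Only adjudicated events will be included in analyses" and "For subjects with more than one event, the earliest of the event dates will be used". Subjects without an event are censored at last contact, and no other censoring rule is given. There is no analysis by component, no cardiovascular-death analysis and no competing-risk handling.

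Elsewhere the SAP is explicit about cause of death. The primary endpoint in Section 2.1.1 opens with the item "Death (all-cause", so marked. Section 8.3.1 separates liver-related death and says that "non-liver-related death will be considered a competing risk". Section 9.2.3 also defines a cardiovascular adverse event of special interest by MedDRA queries, and Section 9.2.4 tabulates it descriptively.

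**The concern.** Section 3 describes the population as "subjects with PBC who are at higher risk of liver-related clinical complications". In such subjects a material share of deaths may be hepatic. Death is also a component of the efficacy composite, on which the trial hopes to show benefit. If the death component of MACE is not restricted, that hoped-for benefit enters the cardiovascular safety test, and the null being tested is equal hazards of any death, MI or stroke.

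Two errors become possible. If OCA raises cardiovascular risk while lowering other mortality, the effects offset each other and the hazard ratio moves toward 1. If OCA has no cardiovascular effect but lowers other mortality, the analysis can report a significant MACE reduction that is not cardiovascular. If OCA leaves other mortality unchanged, a true cardiovascular signal is still diluted.

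**Working it through.** **The plan's own figure.** The SAP gives no event count or power for MACE. Its only power statement (Section 3.2) is 127 events for 80% power at HR 0.60, two-sided 5%, 1:1. Freedman's formula gives (1.960 + 0.842)² × (1.60/0.40)² = 7.85 × 16 ≈ 126, and Schoenfeld's gives 121, so the figure reproduces. That HR of 0.60 belongs to a composite of death, transplant, MELD ≥15, uncontrolled ascites and hospitalisations. It is not a mortality hazard ratio, and the documents contain none.

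**Inputs for MACE**
- From the documents: about 334 subjects enrolled (Clinical Pharmacology Analysis Plan, Section 5); 1:1 allocation (SAP Section 3.1); two-sided 0.05 by default (SAP Appendix A).
- Assumed: mean follow-up 4.9 years, as uniform censoring from 1 to 8.8 years; placebo hazards of 0.03/yr for non-cardiovascular death and 0.01/yr for cardiovascular events; non-cardiovascular death HR of 0.60, 0.80 or 1.0.

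**Approximate hazard ratio of the composite as worded.** Let f be the cardiovascular share of first MACE events on placebo. Then

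HR(composite) ≈ f × HR(CV) + (1 − f) × HR(non-CV death).

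With the assumed hazards, f = 0.01/(0.01 + 0.03) = 0.25.

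| Non-CV death HR | Composite HR, true CV HR 2 | Composite HR, true CV HR 1 |
|---|---|---|
| 0.60 | 0.25×2 + 0.75×0.60 = 0.95 | 0.25 + 0.75×0.60 = 0.70 |
| 0.80 | 0.50 + 0.60 = 1.10 | 0.25 + 0.60 = 0.85 |
| 1.0 | 0.50 + 0.75 = 1.25 | 1.00 |

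A doubled cardiovascular hazard gives a composite HR of exactly 1 when f = (1 − 0.60)/(2 − 0.60) = 0.286, or when f = (1 − 0.80)/(2 − 0.80) = 0.167 for a non-cardiovascular death HR of 0.80. With that HR at 1.0, the composite HR is 1.2 at f = 0.2 and 1.5 at f = 0.5.

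**Simulation of the same case.** Exponential times, unstratified log-rank, two-sided 0.05:

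| Non-CV death HR | Power for harm at CV HR 2, as worded | Same, CV death only | False benefit at CV HR 1, as worded |
|---|---|---|---|
| 0.60 | about 1% | about 35% | about 23% |
| 0.80 | about 6% | about 34% | about 8% |
| 1.0 | about 15% | about 36% | about 2.5% (nominal) |

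**Power after a fix.** Events for 80% power at HR 2: 4 × (1.960 + 0.842)²/(ln 2)² = 4 × 7.85/0.480 ≈ 65.3, so 66 cardiovascular events. The assumed case yields about 22.

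**The case against.** A reader might infer that the SAP defines MACE with all-cause death. It does not say so. It writes all-cause where it means it, as in Section 2.1.1, and here the word stands under a cardiovascular heading, with only adjudicated events counting. The unseen charter may limit qualifying deaths to cardiovascular ones. That stands, and it limits the point to an unrestricted definition. It does not remove the point: if the charter narrows death, Section 9.3 misdescribes its endpoint and does not say how other deaths are handled.

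A reader might also infer that the test mainly measures liver mortality. No figure in the documents shows this. With placebo hazards of 0.02/yr for each cause, a cardiovascular HR of 2 and a non-cardiovascular death HR of 0.60, the simulated trial has about 43 cardiovascular events against 23 other deaths.

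The largest distortions need a mortality HR near 0.60, which the SAP assumes only for the liver composite. At 0.80 they shrink, and at 1.0 there is no false benefit beyond the nominal rate. Follow-up is also assumed. Section 14.1 reports high discontinuation, and Section 9 excludes data after commercial OCALIVA starts. With 0.5 to 5 years of follow-up, and a non-cardiovascular death HR of 0.60, false benefit falls to about 16% and power after the fix to about 21%.

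The cardiovascular tables of adverse events of special interest are a partial safeguard, since they are not driven by liver deaths. They are descriptive, query-based and unadjudicated.

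Finally, counting all deaths avoids misclassifying their cause. That supports keeping such a version, but not having it as the only one.

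**Conclusion.** The point holds in a limited form. Section 9.3 leaves the death component unrestricted and plans nothing that would separate cardiovascular from other mortality. Followed as written, the hazard ratio cannot be read as a cardiovascular effect.

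The size depends on inputs the documents do not give: causes of death, MACE counts and the effect on non-cardiovascular mortality. Cancellation or reversal of a cardiovascular signal requires a real mortality benefit and a low cardiovascular share of events. Otherwise the signal is diluted. The documents do not establish that a doubled risk would be hidden, nor that most MACE would be liver deaths.

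This concerns a safety endpoint and leaves the primary efficacy analysis untouched. It should be corrected because the ambiguity is avoidable and Section 8.3.1 already separates deaths by cause.

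**What to change.** In Section 9.3:
- Define MACE as adjudicated cardiovascular death, MI and stroke.
- Censor non-cardiovascular deaths at the date of death in the stratified log-rank and Cox models, and show their cumulative incidence as a competing event.
- Tabulate each component by arm.
- Keep the version with death from any cause as a supportive analysis.
- Align the wording with the Cardiovascular Adjudication Committee charter, and confirm that the committee classifies cause of death.

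The cost is SAP wording and a few tables if cause is already classified. The SAP does not say whether it is; if not, deaths would need that classification. The statistical price is fewer events, a wider confidence interval and reliance on cause-of-death judgements. The change removes the mixing but does not ensure power, so the cardiovascular hazard ratio should be read mainly through its confidence interval.
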